#### **8.6.3. Stopping Rule for Platelet Count Results**

In the event of a confirmed platelet count less than  $75,000/\text{mm}^3$ , dosing of a subject with Study Drug (ION-827359 or placebo) will be stopped permanently. The platelet count should be tested weekly until it is above  $100,000/\text{mm}^3$  then subsequent monitoring should be per the schedule of procedures.

#### **8.6.4. Stopping Rule for Serum Potassium**

In the event of a laboratory result demonstrating a severe elevation of serum potassium ( $> 5.6 \text{ mmol/L}$ ) at any time point, which was confirmed on reanalysis, dosing of the subject will be stopped permanently unless there is a clear etiology explaining the observed increase.

### **8.7. Adjustment of Dose and/or Treatment Schedule**

There is no adjustment of dose and/or treatment schedule.

### **8.8. Discontinuation of Study Drug/Treatment**

A subject must permanently discontinue study treatment for any of the following:

- The subject becomes pregnant. Report the pregnancy according to instructions in Section 9.5.4
- The subject withdraws consent
- The subject experiences an AE that necessitates permanent discontinuation of Study Drug
- The subject develops laboratory test abnormalities that meet any of the stopping rules listed in Sections 8.6.1 to 8.6.3
- The subject experiences an AE that necessitates unblinding of the Investigator to the subject's treatment assignment
- Subject has PCR test positive for SARS-CoV-2

The reason for discontinuation of Study Drug must be recorded in the electronic Case Report Form (eCRF) and source documentation.

Patients who discontinue Study Drug will remain in the study and continue protocol required tests and assessments will enter the Post-Treatment Period unless consent is withdrawn. For patients withdrawn for reasons other than withdrawal of consent every effort should be made to complete the early termination of study procedures and observations at the time of withdrawal (see [Appendix A](#)) and ideally within 2 weeks from the last dose of Study Drug. If the patient declines or is unable to participate in the above, the Investigator should clarify what type of follow-up the subject is agreeable to: in person, by phone/mail, through family/friends, via correspondence/communication with other physicians, and/or from review of the medical records. Wherever possible these patients should continue to be followed up via the agreed means to collect information on AEs, concomitant medications and survival status. At the very least, the patient's status at the end of the protocol defined Study Period should be ascertained and documented wherever possible. The agreed means of follow-up will be documented in the patient records and notified to the Sponsor.

## **8.9. Withdrawal of Patients from the Study Procedures**

Patients must be withdrawn from study procedures for any of the following:

- Withdrawal of consent
- The subject is unwilling or unable to comply with the protocol

Other reasons for withdrawal of patients from study procedures might include:

- At the discretion of the Investigator for medical reasons
- At the discretion of the Investigator or Sponsor for noncompliance
- Significant protocol deviation

All efforts will be made to complete and report the observations as thoroughly as possible up to the date of withdrawal. All information, including the reason for withdrawal from study, must be recorded in the eCRF as appropriate.

Any subject who withdraws consent to participate in the study will be removed from further treatment and study observation immediately upon the date of request. These patients should be encouraged to complete the early termination study procedures and observations at the time of withdrawal ([Appendix A](#)).

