## PROTOCOL SYNOPSIS (Continued)

Study Visit Schedule and Procedures (Continued)	
Treatment: Study Days 1 to 85
 
Eligible patients will be randomized 2:2:1:1 to ION-827359 (37.5 or 75 mg) or matching placebos. Patients will receive nebulized doses of Study Drug once weekly starting on Study Day 1. Both in-clinic and at-home dosing of ION-827359 will be performed. Patients will record their symptoms in a daily electronic diary and return for study visits to include monitoring and spirometry. There are 3 subset studies:
 

1. A subset of up to about 24 patients will have PK profile sampling performed after the first and last dose

2. A subset of up to about 60 patients will have low dose inspiratory and expiratory HRCT scans to assess regional lung ventilation performed before and post-treatment

3. A subset of up to about 18 patients will undergo bronchoscopy and BAL for target engagement and inflammatory biomarkers before and post-treatment

 
A patient may be enrolled in a maximum of 1 subset study
 
Post-Treatment: Study Days 86 to 162
 
Patients are to return to the Study Center for post-treatment visits on Study Days 92, 120 and 162.
 
Patients that discontinue treatment are encouraged to remain in the study for the Post-Treatment Evaluation Period and will conduct procedures outlined at Study Day 92 visit upon discontinuation of Study Drug.
 
Patients will continue their stable COPD medication regimen throughout the study (screening treatment and post-treatment periods).

Primary Endpoints	Change from Baseline to the primary time point (defined as the average of Weeks 13 and 14) in FEV 1 compared to placebo
Secondary Endpoints	

• Change from Baseline in the E-RS (evaluating respiratory symptoms) daily symptom diary to the primary time point

• Change from Baseline in the CAT to the Week 14 time point

• Change from Baseline in SGRQ to the Week 14 time point

• Change from Baseline in post-bronchodilator FEV1

• Pharmacokinetics

• Incidence and severity of treatment-emergent adverse events (TEAE)

• Abnormal findings in laboratory assessments, ECG, and vital signs

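### Protocol 8.9 makes exit from study procedures mandatory, with no threshold, for patients who cannot or will not follow the protocol; this conflicts with 8.8 and costs their remaining scheduled visits

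*Combined protocol and SAP*

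**What the plan says.** Protocol 8.9 opens with "Patients must be withdrawn from study procedures for any of the following" and gives two triggers. One is withdrawal of consent. The other is "The subject is unwilling or unable to comply with the protocol". Neither a definition nor a threshold is attached. A second list in the same section, worded as possible reasons only, includes "At the discretion of the Investigator or Sponsor for noncompliance" and a significant protocol deviation. For those who leave, 8.9 adds: "All efforts will be made to complete and report the observations as thoroughly as possible up to the date of withdrawal".

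Protocol 8.8 deals with patients who stop treatment: "Patients who discontinue Study Drug will remain in the study and continue protocol required tests and assessments". The exception stated there is withdrawal of consent. The synopsis is softer but points the same way: "Patients that discontinue treatment are encouraged to remain in the study for the Post-Treatment Evaluation Period".

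Section 8.8 also provides for people who leave on other grounds: "For patients withdrawn for reasons other than withdrawal of consent every effort should be made to complete the early termination of study procedures", ideally within two weeks of the last dose. If that is declined or impossible, the site agrees a form of contact: "Wherever possible these patients should continue to be followed up via the agreed means to collect information on AEs, concomitant medications and survival status".

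**The concern.** The two sections give different instructions for the same patient. Someone who has stopped Study Drug and also falls short on another requirement, such as the diary or some visits, is to stay under 8.8 and must leave under 8.9. Because the trigger has no threshold, one site may read a lapse as inability to comply (exit mandatory), another as noncompliance (exit discretionary), and a third may simply apply 8.8.

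The clause matters only for patients who would still attend something. A patient who refuses all contact is lost whatever the text says. For the rest, follow-up ends by instruction and not by the patient's choice. If difficulty with an inhaled weekly treatment goes with poor tolerability or falling lung function, the missing values could depend on outcome and on arm.

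The protocol has little to absorb this. Withdrawn patients are not replaced (4.3). The only stated sensitivity analysis of the primary MMRM is a repeat in the per-protocol set (10.6.3.1). The SAP's missing-data section (3.1.5) covers questionnaire items, not absent FEV1.

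**Working it through.** **1. The plan's own figure.** Inputs from protocol 10.2: difference 100 mL, SD 220 mL, two-sided alpha 0.05, 116 pooled active against 58 pooled placebo.
- SE = 220 × √(1/116 + 1/58) = 35.4 mL.
- Power = Φ(100/35.4 − 1.96) = Φ(0.867) = 80.7%. The noncentral t version gives 80.3%. Both meet the stated 80%.
- Enrolment = 174/0.97 = 179.4, rounded up to 180. The allowance is therefore 180 − 174 = 6 patients.

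Nothing in the sample-size section is wrong because of this point.

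**2. The clauses side by side.**

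| Situation, consent not withdrawn | 8.8 | 8.9 |
|---|---|---|
| Stopped Study Drug, otherwise compliant | Stays in assessments | Silent, unless stopping counts as inability to comply |
| Stopped Study Drug, cannot or will not meet another requirement | Stays in assessments | Must leave study procedures |
| Noncompliant | Not addressed | Discretionary in one list; mandatory in the other if it amounts to unwillingness or inability |

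The second row is a direct conflict. The third is a conflict inside 8.9.

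**3. What a patient who leaves early loses.** SAP 3.1.1 maps spirometry to Week 13 on Days 72–88 and to Week 14 on Days 89–99. Suppose the last dose is on Day 36 and the early termination visit takes place by Day 50 (36 + 14). Its FEV1 then falls in the Week 7 window (Days 37–50) and cannot supply the primary time point. The fallback contact in 8.8 names adverse events, medication and survival; it does not name spirometry or laboratory tests. The Day 120 and Day 162 visits also drop out.

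**4. Precision if more than 3% are lost.** The loss rate is an assumption, because the documents give none. I take 180 enrolled, loss equal across arms, and the formula in step 1.

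| Loss | Evaluable | Power |
|---|---|---|
| 3% | 174.6 | 80.8% |
| 5% | 171 | 80.0% |
| 10% | 162 | 77.9% |
| 15% | 153 | 75.5% |
| 20% | 144 | 73.0% |

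These figures measure lost precision only. They say nothing about bias.

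**5. How far the final SAP limits the effect.** After early discontinuation, SAP 3.1.1 maps an assessment to an analysis visit only if it falls within 14 days of the last dose and inside the window. On target days, a last dose on Day 57 reaches Day 71 at most (57 + 14), one day short of the Week 13 window. A patient who stopped dosing on or before Day 57 therefore adds nothing to the Week 13/14 summary, retained or not. For those who have stopped drug, retention can change that summary only if the last dose was on Day 64 or later. In addition, SAP 3.3 makes efficacy descriptive and drops the models, with 60 randomized, 59 dosed and 10 through Week 14.

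Post-treatment data are still used. SAP 3.1.1 summarises post-treatment efficacy by visit label, and the definition of a treatment-emergent event in SAP 3.4.2 has no end date.

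**The case against.** The strongest reply is that 8.8 and 8.9 have different subjects, stopping drug and leaving procedures, and that 8.8 already looks after those who leave. Much of this stands. The early termination visit is the Day 92 visit and includes spirometry, chemistry and haematology (Appendix A). Patients who leave during the post-treatment period are asked for the Day 162 procedures (6.1.4). Serious events are followed to resolution (9.4.1). The per-protocol set requires at least 9 doses within the full analysis set (10.3), so the plan expects under-dosed patients to remain in the primary population.

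Three stronger readings are therefore not supported:
- A reader might infer that these patients lose their FEV1 and safety data by rule. They do not: earlier data are kept and an exit visit is requested. What goes is the remaining schedule.
- A reader might infer that 8.8 allows no exit except withdrawal of consent. Its own text provides for patients withdrawn on other grounds.
- A reader might infer that a patient who misses doses or cannot tolerate nebulisation must leave. The first may fall under the discretionary bullet and the second under 8.8; the clause is too vague to decide.

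What the reply does not remove is the word must, attached to an undefined trigger, beside a retention rule and a discretionary bullet that point the other way. One exit visit does not replace Week 13/14 FEV1 or the later safety visits.

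**Conclusion.** The point holds as a conflict between 8.8 and 8.9, and within 8.9, that can end scheduled follow-up without withdrawal of consent. The loss is limited to visits after withdrawal.

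Its size is unknown. It is tempting to say that the clause breaches the 3% allowance; it could exceed it, but no withdrawal rate is given. It is also tempting to put a figure on the bias: if 5–15% of active patients left, none on placebo, and their FEV1 change was 100–200 mL worse, the active mean would be overstated by 0.05 × 100 = 5 mL to 0.15 × 200 = 30 mL. Every one of those inputs is invented. The product also describes a mean that ignores the leavers altogether, whereas the protocol's MMRM would use their earlier visits. That loss would be related to outcome is plausible, not documented.

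For the trial as finally analysed, the effect on the FEV1 summary is small. The effect on safety follow-up is more relevant: SAP 1.1 stops treatment partly because of a chronic toxicology finding and has patients then on treatment continue through the 10-week post-treatment period, which 8.9 could cut short.

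**What to change.** Reconcile 8.9 with 8.8. Make withdrawal of consent the only mandatory reason for leaving study procedures. State that noncompliance or a protocol deviation is recorded but does not by itself end data collection, and that scheduled spirometry, diary, laboratory and adverse event assessments continue as far as the patient agrees. Leave Investigator discretion for medical reasons and every rule for stopping Study Drug as they are; the change concerns data collection only.

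The cost is protocol wording, some extra visits, and some off-drug or poorly adherent data points.

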## **8.10. Concomitant Therapy and Procedures**

The use of concomitant therapies or procedures defined below must be recorded on the subject's eCRF. Adverse events related to administration of these therapies or procedures must also be documented on the appropriate eCRF.

### **8.10.1. Concomitant Therapy**

A concomitant therapy is any non-protocol specified drug or substance (including over-the-counter medications, herbal medications and vitamin supplements) administered between Screening and the last visit (Visit 11).

### **Allowed Concomitant Therapy**

Any other medications deemed necessary by the Investigator are allowed except those listed in the disallowed concomitant therapy.

### **Disallowed Concomitant Therapy**

The following are disallowed concomitant therapies:

- Oral corticosteroids
- Theophylline
- Roflumilast
- See [Table 1](#), Section 6.1.3 for bronchodilator use prior to visits

### **8.10.2. Concomitant Procedures**

A concomitant procedure is any therapeutic intervention (e.g., surgery/biopsy, physical therapy) or diagnostic assessment (e.g., blood gas measurement, bacterial cultures) performed between Screening and last study visit (Visit 11).

## **8.11. Treatment Compliance**

Compliance with treatment dosing is to be monitored and recorded in the eCRF by Study Center staff.

Patients will record treatment in a dosing diary that will be reviewed periodically by Study Center staff and the Clinical Monitor.

## **9. SERIOUS AND NON-SERIOUS ADVERSE EVENT REPORTING**

### **9.1. Sponsor Review of Safety Information**

Safety information will be collected, reviewed, and evaluated by the Sponsor or designee in accordance with the applicable Ionis and/or designee SOPs throughout the conduct of the clinical trial.

### **9.2. Regulatory Requirements**

The Sponsor or designee is responsible for regulatory submissions and reporting to the Investigators of SAEs including SUSARs per the International Conference on Harmonization (ICH) guidelines E2A and ICH Good Clinical Practice (GCP). Country-specific regulatory requirements will be followed in accordance with local country regulations and guidelines.

Institutional Review Boards (IRB)/Independent Ethics Committees (IEC) will be notified of any SAE according to applicable regulations.

In addition to the Investigator's assessment of relatedness, the Sponsor or designee will evaluate the available information and perform an independent assessment of all reported SAEs and determine if there is a reasonable possibility that the Study Drug (ION-827359 or placebo) is causally related to a reported SAE. While the Sponsor may upgrade an Investigator's decision it

is not permissible to downgrade the Investigator's opinion for the purposes of determining whether the SAE meets the definition of a SUSAR.

The Sponsor or designee will evaluate the available information for all reported SAEs and decide if there is a reasonable possibility that the Study Drug (ION-827359 or placebo) caused the AE and, therefore, meets the definition of a SUSAR.

Appropriate personnel at the Sponsor or designee will unblind SUSARs for the purpose of regulatory reporting. The Sponsor or designee will submit SUSARs to Regulatory Agencies in blinded or unblinded fashion according to local law. The Sponsor or designee will submit SUSARs to Investigators in a blinded fashion.

For the purpose of regulatory reporting of SUSARs, there are no "expected" AEs in this study population. For Study Drug (ION-827359 or placebo) "expected" AEs, refer to the Investigator's Brochure.

The Sponsor or designee will monitor these protocol-specified SAEs using the incidence rate of the event compared to the rate expected in a non-Study Drug exposed population. If the aggregate analysis indicates that an event is occurring more frequently or at a greater severity than expected, then the event will be reported.

SAEs will be evaluated on a case by case basis to determine whether there is a reasonable possibility that the drug caused the event. If the event is considered by the Sponsor or designee to meet the definition of a SUSAR, the event will be reported.

## **9.3. Definitions**

### **9.3.1. Adverse Event**

An AE can be any unfavorable and unintended sign (including an abnormal laboratory finding, for example), symptom, or disease temporally associated with the use of medicinal (investigational) product, whether or not the AE is considered related to the medicinal (investigational) product.

An AE can therefore be any of the following:

- Any unfavorable and unintended sign (including an abnormal laboratory finding), symptom, or disease temporally associated with the use of a medicinal product, whether or not considered related to the medicinal product
- Any new disease or exacerbation of an existing disease (a worsening in the character, frequency, or severity of a known condition)
- Recurrence of an intermittent medical condition (e.g., headache) not present at Baseline
- Any deterioration in a laboratory value or other clinical test (e.g., ECG, X-ray) that is associated with symptoms or leads to a change in study treatment or concomitant treatment or discontinuation from Study Drug
- Adverse events that are related to a protocol-mandated intervention, including those that occur prior to assignment of study treatment (e.g., screening invasive procedures such as biopsies)

### 9.3.2. Adverse Drug Reaction and Suspected Unexpected Adverse Drug Reaction

#### Adverse Drug Reaction (ADR)

In the *pre-approval* clinical experience with a new medicinal product or its new usages, particularly as the therapeutic dose(s) may not have been established, ADR is defined as follows:

All noxious and unintended responses to a medicinal product related to any dose should be considered adverse drug reactions.

The phrase "responses to a medicinal product" means that a causal relationship between the medicinal product and the AE has been determined by the Sponsor as at least a reasonable possibility, i.e., the relationship cannot be ruled out.

#### Suspected Unexpected Adverse Drug Reaction

A suspected unexpected ADR is any ADR, the nature or severity of which is not consistent with the applicable product information, e.g., Investigator's Brochure for an unapproved medicinal (investigational) product.

A suspected adverse reaction implies a lesser degree of certainty about causality than an adverse reaction.

### 9.3.3. Serious Adverse Event (SAE)

A SAE is any AE that in the view of either the Investigator or Sponsor, meets any of the following criteria:

- Results in death
- Is life threatening: that is, poses an immediate risk of death at the time of the event  
An AE or suspected adverse reaction is considered "life-threatening" if, in the view of either the Investigator or Sponsor, its occurrence places the subject at immediate risk of death. It does not include an AE or suspected adverse reaction that, had it occurred in a more severe form, might have caused death
- Requires inpatient hospitalization or prolongation of existing hospitalization  
Hospitalization is defined as an admission of greater than 24 hours to a medical facility and does not always qualify as an AE
- Results in a persistent or significant incapacity or substantial disruption of the ability to conduct normal life functions
- Results in a congenital anomaly or birth defect in the offspring of the subject (whether the subject is male or female)
- Important medical events that may not result in death, are not life-threatening, or do not require hospitalization may also be considered serious when, based upon appropriate medical judgment, they may jeopardize the subject and may require medical or surgical intervention to prevent 1 of the outcomes listed in this definition. Examples of such medical events include allergic bronchospasm requiring intensive treatment in an emergency room or at home, blood dyscrasias or convulsions that do not result in inpatient hospitalization, or the development of drug dependency or drug abuse

The terms "severe" and "serious" are not synonymous. Severity refers to the intensity of an AE (e.g., rated as mild, moderate, or severe, or according to National Cancer Institute Common Terminology Criteria for Adverse Events [NCI CTCAE]; OR Toxicity Grading Scale for Healthy Adult and Adolescent Volunteers Enrolled in Preventive Vaccine Clinical Trials; the event itself may be of relatively minor medical significance (such as severe headache without any further findings).

Severity and seriousness need to be independently assessed for each AE recorded on the eCRF.

## **9.4. Monitoring and Recording Adverse Events**

Any pre-existing conditions or signs and/or symptoms present in a subject prior to the start of the study (i.e., before informed consent) should be recorded as Medical History and not recorded as AEs unless the pre-existing condition worsened. The Investigator should always group signs and symptoms into a single term that constitutes a **single unifying diagnosis** if possible. Before a diagnosis is confirmed, all symptoms should be reported as separate AEs.

